9.3.2.3 Correlation analysis

Correlation analysis using both Pearson's correlation coefficient and Spearman's correlation coefficient will be evaluated for the following endpoints for their corresponding change from baseline to week 24. Correlation analysis will be performed by treatment arms as well as in the overall patient population.

Percentage change of VO₂max and percentage change of ppFEV1

Absolute change of VO₂max and absolute change of ppFEV1

Percentage change of exercise duration and percentage change of ppFEV1

Absolute change of exercise duration and absolute change of ppFEV1

Absolute change of VO₂ at AT and absolute change of ppFEV1

Percentage change of VO₂ at AT and percentage change of ppFEV1

Absolute change of functional VO₂ gain and absolute change of ppFEV1

Percentage change of functional VO₂ gain and percentage change of ppFEV1

Absolute change of the slope of pulmonary ventilation (VE) versus carbon dioxide production (VCO₂) and absolute change of ppFEV1

Percentage change of the slope of pulmonary ventilation (VE) versus carbon dioxide production (VCO₂) and percentage change of ppFEV1

Absolute change of sleeping time and absolute change of ppFEV1

Absolute change of physical activity and absolute change of ppFEV1

Absolute change of time above sedentary duration and absolute change of ppFEV1

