5 INTRODUCTION

5.1 Study Rationale

This study is designed to evaluate the effect of lumacaftor/ivacaftor (LUM/IVA) combination therapy on exercise tolerance in subjects with cystic fibrosis (CF). Patients with CF exhibit exercise intolerance, and although pulmonary symptoms are partially responsible, cardiovascular or myopathic factors are believed to be the major limitation in patients with milder disease.^{1,2}

Exercise capacity, as measured by maximal oxygen consumption (VO_{2max}) during cardiopulmonary exercise tests (CPETs), has been demonstrated to be a significant predictor of mortality in patients with CF.^{3,4} A randomized crossover study⁵ and published case series^{6,7} suggest that ivacaftor (IVA) may improve VO_{2max} and other measures of exercise capacity. These findings may be independent of improvements in forced expiratory volume in 1 second (FEV_1) previously demonstrated with ivacaftor. To date, there has been no prospective randomized evaluation of LUM/IVA effects on exercise capacity as measured by CPET.

In this study, the CPET will be used to assess improvements in exercise tolerance, as measured by VO_{2max} , after up to 24 weeks of LUM/IVA therapy. The study population will be patients with CF who are 12 years of age and older and are homozygous for the *F508del-CFTR* mutation.

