12.1 Sample Size and Power

Assuming a common standard deviation (SD) of 10% for the primary efficacy endpoint and a dropout rate of 10%, a sample size of 33 subjects in each treatment group would provide at least 80% power to detect a difference of 7.5% between the means for the 2 treatment groups using a 2-sided test at the 0.05 significance level. If the true difference is smaller, or if there is greater variability, a larger sample size would be required to provide 80% power.

Table 12-1 shows the required sample sizes for various assumptions about the true treatment effect using a 2-sided test at the 0.05 significance level.

Because LUM/IVA has recently been approved in several countries, it is expected that additional data, independent of this study, will emerge while this study is underway and will allow more precise estimation of the true treatment effect. The final sample size will be based on these data, and the protocol may be amended as appropriate.

Table 12-1 Sample Sizes for 80% Power

True Difference Between Placebo and LUM/IVA Effects on Primary Endpoint	Sample Size Needed for 80% Power (subjects per treatment group)
5.0%	72
5.5%	59
6.0%	50
6.5%	44
7.0%	38
7.5%	33

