12.3.3.3 Correlation Analyses

The correlations between changes in exercise tolerance assessments and changes in selected efficacy outcome measures, including ppFEV₁ and BMI, will be calculated for each treatment group.

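### The SAP's correlations over the whole study population are not adjusted for treatment, so they mix the within-arm association with the difference between arms (minor)

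*SAP*

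**What the plan says.** Protocol 12.3.3.3 plans correlations between changes in exercise tolerance and changes in selected efficacy measures, including ppFEV1 and BMI, and says that they "will be calculated for each treatment group".

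SAP 9.3.2.3 keeps that and extends it: "Correlation analysis will be performed by treatment arms as well as in the overall patient population". On method it says only this: "Correlation analysis using both Pearson's correlation coefficient and Spearman's correlation coefficient will be evaluated". It names no partial, stratified or treatment-adjusted coefficient. It lists 13 pairs, and change in ppFEV1 is one member of every pair. Two of the 13 use the VE/VCO2 slope, for example "Percentage change of the slope of pulmonary ventilation (VE) versus carbon dioxide production (VCO₂) and percentage change of ppFEV1".

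The SAP gives no hypothesis, P value or threshold for these correlations. It does not say whether the by-arm or the overall coefficient is the basis for interpretation.

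**The concern.** A correlation computed over two randomized arms combined has two sources: the association between subjects within an arm, and the difference between the arm means. If LUM/IVA changes both members of a pair, the second source alone yields a non-zero coefficient. A reader who sees only the overall value cannot tell whether subjects with a larger gain in ppFEV1 also had a larger gain in exercise capacity, or whether the drug simply moved both averages.

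The background makes that distinction of interest. Of the earlier ivacaftor reports on exercise capacity, Protocol 5.1 says: "These findings may be independent of improvements in forced expiratory volume in 1 second". If the drug improves both VO2max and ppFEV1, the overall coefficient leans towards a link between them for a reason unrelated to the within-arm association. It also rests on twice as many subjects as either by-arm value, so it may look like the firmest of the three.

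**Working it through.** **Inputs from the documents.** Protocol 12.1 assumes an SD of 10% for percentage change in VO2max and 10% dropout, and is designed to detect "a difference of 7.5% between the means for the 2 treatment groups using a 2-sided test at the 0.05 significance level". It states that "a sample size of 33 subjects in each treatment group would provide at least 80% power".

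**The plan's own figure first.** A two-sided t-test at 5% with 80% power and a standardized difference of 7.5/10 = 0.75 needs 29 completers per group. 29/0.9 = 32.2, rounded up to 33, as stated. The same method reproduces all six rows of Table 12-1 (72, 59, 50, 44, 38, 33). With 33 × 0.9 = 29.7 completers per group, power is about 0.81. The sample size itself is not in question; it supplies d1 = 0.75 for VO2max and about 30 completers per arm.

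**Assumed input.** The documents give neither an effect nor an SD for change in ppFEV1. Its standardized effect d2 is therefore an assumption, shown over a range.

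**Formula.** For 1:1 arms with within-arm correlation r and standardized effects d1 and d2:

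pooled r = (r + d1·d2/4) / √[(1 + d1²/4)(1 + d2²/4)]

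With r = 0 the sign is that of d1·d2, and the value is zero if either effect is zero.

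**Numbers in, with r = 0 and d1 = 0.75, so that 1 + d1²/4 = 1.1406:**

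- d2 = 0.3: 0.0563/√(1.1406 × 1.0225) = 0.052
- d2 = 0.5: 0.0938/√(1.1406 × 1.0625) = 0.085
- d2 = 0.75: 0.1406/1.1406 = 0.123
- d2 = 1.0: 0.1875/√(1.1406 × 1.25) = 0.157
- d2 = −0.5: −0.085

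**Simulation** (30 per arm, 20,000 trials, normal data, zero within-arm correlation, d1 = 0.75). The adjusted columns use the Pearson correlation of arm-centred changes.

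| d2 | mean pooled Pearson (Spearman) | share of trials with r > 0 | pooled: nominal 5% rejection | adjusted: mean r | adjusted: rejection |
|---|---|---|---|---|---|
| 0.25 | 0.044 (0.043) | 63% | 6% | 0.00 | 5% |
| 0.5 | 0.087 (0.085) | 75% | 10% | 0.00 | 5% |
| 0.75 | 0.125 (0.123) | 84% | 16% | 0.00 | 5% |
| 1.0 | 0.158 (0.158) | 90% | 23% | 0.00 | 5% |
| −0.5 | −0.086 (−0.083) | 25% | 10% | 0.00 | 5% |

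At d2 = 0.3, a separate run of the same size gave 6.4% rejection pooled and 5.0% adjusted. The sampling SD of pooled r is 0.12 to 0.13 throughout, so the average shift for d2 from 0.3 to 1.0 is about 0.4 (0.052/0.13) to 1.3 (0.157/0.124) sampling SDs.

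**If the within-arm correlation is not zero.** With r = 0.3 and d1 = 0.75, pooled r is 0.187, 0.281, 0.358 and 0.408 for d2 = −0.5, 0, 0.5 and 1.0. The arm difference distorts a real association too. When only one mean moves, no correlation is created, but an existing one is slightly diluted (0.30 to 0.281).

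**The case against.** The strongest reply is that the sentence that adds the overall coefficient also keeps the by-arm ones. These are free of the artefact, and a gap between the by-arm and overall values will be visible for every pair. SAP section 4 expressly allows supportive analyses beyond the protocol, so a reader who infers a breach of the protocol goes too far. The overall coefficient is also a legitimate description of the marginal association in the trial population, including covariation that treatment produces; it misleads only if read as the within-arm association. All of this stands. It makes the point small, but it does not tell the reader which value to interpret.

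Several stronger readings are tempting, and the documents do not support them.

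- *The artefact is always positive.* It takes the sign of d1·d2. For the two VE/VCO2-slope pairs, if a lower slope means better ventilation (an assumption; Protocol 8.2.3 says only that the slope measures ventilatory efficiency), benefit on both variables pushes the coefficient down.
- *It distorts an association within subjects.* Each subject contributes one pair of changes, so the association at issue is between subjects within an arm.
- *The rejection rates describe a planned test.* The SAP specifies none. The rates matter only if P values are attached to the coefficients.
- *The trial sets out to test whether exercise gains are independent of FEV1.* Protocol 5.1 comments on earlier ivacaftor findings; the objectives in Protocol section 6 pose no such question.
- *The overall coefficient will be the one quoted.* It has the largest n, but nothing in the documents says it will be preferred.

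**Conclusion.** The point holds as a minor one. The overall correlations in SAP 9.3.2.3 are an unadjusted addition to the protocol's by-group plan, and they confound the within-arm association with the treatment effect whenever treatment moves both variables. With no within-arm correlation and the plan's design effect on VO2max, the average distortion is about 0.05 to 0.16 in r for ppFEV1 effects of 0.3 to 1.0 SD. Even 0.157 corresponds to an r² of only 0.157² = 0.025. It is an expected value and need not show in a given trial.

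The size rests on assumptions: the ppFEV1 effect is not in the documents, and d1 = 0.75 applies only to percentage change in VO2max, which is in one of the 13 pairs. For the other 12 the documents give no design effect, so only the direction rule carries over. No primary or key secondary conclusion depends on this analysis.

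**What to change.** In SAP 9.3.2.3, keep the by-arm Pearson and Spearman coefficients and name them as the basis for interpretation. Replace the overall coefficient with a partial correlation adjusted for treatment arm, in both Pearson and Spearman form. Alternatively, report the partial correlation beside the overall value and label the latter as unadjusted for treatment. State how ranks are formed for the Spearman version.

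The cost is a short method definition and a small program change, with the same subjects and data. There is a gain in precision over a single arm: under zero correlation the SD of r is about 1/√29 = 0.19 with 30 subjects in one arm, against about 1/√58 = 0.13 for the adjusted coefficient with 60. The one drawback is that a single adjusted value assumes the same association in both arms; the by-arm results let the reader check that.

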9.3.2.4 Multiplicity adjustment

No multiplicity adjustment will be made in this study.

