7.2 Secondary Endpoints

Key Secondary Endpoint

- Change from baseline in exercise duration during CPET at Week 24

Other Secondary Endpoints

- Change from baseline in oxygen consumption (VO_2) at anaerobic threshold (AT) (the exercise intensity at which lactate starts to accumulate) at Week 24
- Change from baseline in functional VO_2 gain at Week 24
- Change from baseline in the pulmonary ventilation (VE) versus carbon dioxide production (VCO_2) slope at Week 24
- Change from baseline in percent predicted forced expiratory volume in 1 second (ppFEV₁) at Week 24
- Change from baseline in body mass index (BMI) at Week 24
 - Change from baseline in Cystic Fibrosis Questionnaire-Revised (CFQ-R) respiratory domain score at Week 24
 - Change from baseline in overall Patient Health Questionnaire (PHQ-8) and Generalized Anxiety Disorder (GAD-7) scores at Week 24
- Change from baseline in physical activity as determined by actigraphy at Week 24
- Change from baseline in duration of sleep time and change in sleep quality during the night at Week 24
- Safety and tolerability assessments based on adverse events (AEs), clinical laboratory values (serum chemistry and hematology), vital signs, and ophthalmologic examinations (for subjects under 18 years of age only).

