12.3.1 General Considerations

All individual subject data for the FAS will be presented in data listings.

Continuous variables will be summarized using the following descriptive summary statistics: the number of observations (n), mean, SD, median, minimum value (min), and maximum value (max).

Categorical data will be summarized using counts and percentages.

Baseline for a variable will, unless specifically stated otherwise, be defined as the most recent non-missing measurement (scheduled or unscheduled) collected before the initial administration of study drug. For actigraphy variables, baseline will be the data collected for 1 week during the Screening Period.

Change from baseline will be calculated as post-baseline value minus baseline value.

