12.3.3.2 Analysis of Secondary Efficacy Variables

Key Secondary Efficacy Endpoint:

The key secondary efficacy endpoint is the change from baseline in exercise duration during CPET at Week 24. The same analysis method as for the primary efficacy endpoint will be used, with change from baseline in exercise duration as the dependent variable. To control for multiplicity, the test for change in exercise duration will only be considered statistically significant if the 2-sided *P* value is 0.05 or less and the test for the primary endpoint also is statistically significant.

Other Secondary Efficacy Endpoints:

All other secondary efficacy endpoints will be analyzed in a similar fashion. No adjustment for multiplicity will be made for these endpoints. The other secondary endpoints are listed in Section 7.2.

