4 INTRODUCTION

This SAP describes the planned final analyses for the Study VX15-809-112 data and is based on the

- approved clinical study protocol (Version 1.0, dated 15 January 2016),
- approved electronic case report form (eCRF) (dated 13 January 2017).

Study VX15-809-112 is a Phase 4, Randomized, Double-Blind, Placebo-Controlled, Parallel-Design Study of the Effect of Lumacaftor/Ivacaftor Combination Therapy on Exercise Tolerance in Subjects Aged 12 Years and Older With Cystic Fibrosis, Homozygous for the *F508del-CFTR* Mutation.

This SAP (Methods) documents the planned final statistical analyses of efficacy and safety introduced in the study protocol of VX15-809-112, and describes the corresponding data presentations. It also documents additional efficacy and safety analyses not specified in the protocol, which will provide supportive information to the scientific understanding of the drug entity.

The [REDACTED] Biostatistics Department will perform the statistical analysis of the efficacy and safety data under the supervision of Vertex Biometrics Department; SAS (Version 9.2, or higher) will be used to generate all statistical outputs (tables, figures, listings, and datasets). The SAP will be finalized and approved prior to the final clinical data lock and treatment unblinding for the study.

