6.1.2 Secondary Endpoints

Key Secondary Endpoint

- Relative change from baseline in exercise duration during CPET at Week 24

Other Secondary Endpoints

- Absolute change from baseline in exercise duration during CPET at Week 24
- Absolute change from baseline in VO_2 max during cardiopulmonary exercise testing (CPET) at Week 24
- Absolute and relative change from baseline in oxygen consumption (VO_2) at anaerobic threshold (AT) (the point during exercise at which lactate starts to accumulate) at Week 24
- Absolute and relative change from baseline in functional VO_2 gain at Week 24
- Absolute and relative change from baseline in the slope of pulmonary ventilation (VE) versus carbon dioxide production (VCO_2) at Week 24
- Absolute change from baseline in percent predicted forced expiratory volume in 1 second (ppFEV₁) at Week 24
- Relative change from baseline in percent predicted forced expiratory volume in 1 second (ppFEV₁) at Week 24
- Absolute change from baseline in body mass index (BMI) at Week 24
- Relative change from baseline in body mass index (BMI) at week 24
- Absolute change from baseline in Cystic Fibrosis Questionnaire-Revised (CFQ-R) respiratory domain score at Week 24
- Absolute change from baseline in overall Patient Health Questionnaire (PHQ-8) and Generalized Anxiety Disorder (GAD-7) scores at Week 24
- Absolute change from baseline in total daily physical activity as determined by actigraphy at Week 24
- Relative change from baseline in total daily physical activity as determined by actigraphy at Week 24
- Absolute change from baseline in duration of sleep time during the night at Week 24

- Relative change from baseline in duration of sleep time during the night at Week 24
- Absolute change from baseline in time above sedentary duration at Week 24
- Relative change from baseline in time above sedentary duration at Week 24

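### The SAP drops the protocol's gate on exercise duration and names a different key secondary variable, so duration could be declared significant after a failed primary

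*SAP*

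**What the plan says.** **Multiplicity.** Protocol 12.3.3.2 states a rule for the key secondary endpoint: "To control for multiplicity, the test for change in exercise duration will only be considered statistically significant if the 2-sided" P value is at most 0.05 "and the test for the primary endpoint also is statistically significant". For the other secondary endpoints alone it then says: "No adjustment for multiplicity will be made for these endpoints". SAP 9.3.2.4 consists of one sentence: "No multiplicity adjustment will be made in this study". No other SAP section mentions a testing sequence.

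**The key secondary variable.** Protocol 7.2 lists it as "Change from baseline in exercise duration during CPET at Week 24". Protocol 12.3.1 fixes the meaning of change: "Change from baseline will be calculated as post-baseline value minus baseline value". The protocol's variable is therefore the absolute change. SAP 6.1.2 lists the key secondary as "Relative change from baseline in exercise duration during CPET at Week 24", and SAP 9.3.2 and 9.3.2.1.1 repeat this. Absolute change appears among the other secondary endpoints in SAP 6.1.2, 9.3.2 and 9.3.2.1.2. SAP 9.3.2.2.1, which covers analysis of the key secondary, then takes both forms together and gives both a model like that of the primary. SAP 9.3.1.2 plans a between-arm P value from that model.

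**Status of the SAP.** SAP section 4 says that the plan is based on protocol Version 1.0 and that it adds some analyses. It does not mention withdrawing a decision rule or changing the key secondary variable.

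**The concern.** The protocol offers one confirmatory claim beyond the primary and sets a condition on it. The SAP, which the analysts will follow, omits that condition. If VO2max misses 0.05 and a duration P value does not, the protocol says duration is not significant, while nothing in the SAP prevents the claim.

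Restoring the gate would not settle the matter by itself. The protocol's gate applies to absolute change, whereas the SAP's key secondary is relative change. Dividing by baseline changes each subject's weight in the comparison, so the two forms can give different P values. With both under the key secondary heading, there are two P values and no consistent statement of which one counts. A choice made after the results are seen could not be defended as prespecified.

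**Working it through.** **1. The plan's own figures.** Neither document states a familywise error rate. The only related calculation is the sample size (Protocol 12.1, SAP 7.2): SD 10%, difference 7.5%, two-sided 0.05, 80% power, 10% dropout. A two-sample t calculation needs 29 completers per arm, and 29 / 0.9 = 32.2 rounds up to the stated 33. The same method returns all six rows of the table (72, 59, 50, 44, 38, 33). It involves the primary endpoint alone, so the gate does not affect it.

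**2. Inputs for the error rate.**
- Two-sided 0.05 for each test, critical value 1.96 (Protocol 12.1 and 12.3.3.2).
- Test statistics Z1 (VO2max) and Z2 (duration), jointly normal with correlation ρ. The documents do not give ρ, so a range is assumed.
- Global null: the drug affects neither endpoint.

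**3. With the protocol's gate.** Duration can be significant only when VO2max is. At least one false claim therefore means that VO2max is falsely significant, and the error is 5% at any ρ.

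**4. Without the gate, one duration test.** Error = 1 − P(|Z1| < 1.96 and |Z2| < 1.96). At ρ = 0 this is 1 − 0.95² = 9.75%. The excess over 5% is the chance that duration is called significant after VO2max has failed.

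| Assumed ρ | Error without gate | Error with gate | Excess (percentage points) |
|---|---|---|---|
| 0.5 | 9.1% | 5% | 4.1 |
| 0.7 | 8.3% | 5% | 3.3 |
| 0.8 | 7.8% | 5% | 2.8 |
| 0.9 | 7.0% | 5% | 2.0 |

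The bound under any dependence is 5% + 5% = 10%. Simulated two-sample t tests with 30 per arm (33 × 0.9 = 29.7; 400,000 trials per ρ) gave 9.1%, 8.3% and 7.0% at ρ = 0.5, 0.7 and 0.9 ungated, and 4.9% to 5.0% gated.

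**5. Without the gate, both duration forms.** Let r be the assumed correlation of each form with VO2max and s the assumed correlation between the forms. With s = 0.95, the chance of at least one nominal P below 0.05 among the three tests is 10.3%, 9.5%, 8.9% and 8.0% at r = 0.5, 0.7, 0.8 and 0.9. With s = 0.9 and r = 0.5 it is 10.8%.

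**6. When VO2max truly differs and duration does not.** Assuming 80% power for VO2max, the false-positive rate for one duration test is 5.0% ungated, against 3.4% (ρ = 0.5) or 2.6% (ρ = 0.8) gated. It stays within 5% either way, so the inflation is confined to the case where neither endpoint differs.

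**The case against.** The strongest reply is that a fixed-sequence gate leaves each test at 0.05, so a statement that nothing is adjusted may mean only that alpha is not split. The SAP does not expressly withdraw the gate, it cites the protocol as its basis, and it gives no significance rule of its own for duration. This has some force: the SAP is silent on when duration may be claimed and does not openly authorise the claim. But the protocol presents the gate as its multiplicity control, and the SAP's sentence covers the whole study. Neither document says which prevails, and Protocol section 12 leaves analysis details to the SAP. At best the SAP is ambiguous about a confirmatory claim.

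A second objection concerns the three-test figures, and it stands as a limit on their use. If the second duration form stays among the unadjusted secondary endpoints, the chance of a nominal P below 0.05 for VO2max or for that form is still 7.0% to 9.1% after the fix, by step 4. The 5% applies only to the two-test confirmatory family. The three-test figures show what follows from treating both forms as key, and they are not a level that the fix brings to 5%.

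Third, the correlations are assumed and the excess is only 2.0 to 4.1 percentage points, under the global null. That is correct. The case rests on the contradiction between the documents; the arithmetic shows its size.

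**Conclusion.** The point holds and should be fixed before unblinding. The SAP omits the protocol's condition on the only gated claim, and the documents define the gated variable differently. For VO2max plus one duration test, the error when neither endpoint differs rises from 5% to between 7.0% and 9.1%, for assumed correlations of 0.9 down to 0.5 and jointly normal statistics. It exceeds 5% at any correlation below 1. The absolute-versus-relative mismatch is a separate defect that these two-test figures do not measure. The primary test keeps its 5% level, and the sample size stands.

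**What to change.** Replace SAP 9.3.2.4 with the protocol's sequence:

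1. Test VO2max at two-sided 0.05.
2. Only if it is significant, test one named exercise-duration variable at two-sided 0.05.
3. Report all other secondary endpoints without adjustment, with nominal P values where a test is planned.

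Name the duration variable identically in the protocol and in SAP 6.1.2, 9.3.2, 9.3.2.1.1, 9.3.2.1.2 and 9.3.2.2.1. By default this is the protocol's absolute change. If relative change is intended, record the departure and its reason before unblinding. List and define the other form under the other secondary endpoints, and move its analysis out of SAP 9.3.2.2.1.

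The cost is one SAP paragraph and aligned wording of one endpoint in five SAP sections, or a documented departure from the protocol. Sample size and primary alpha do not change. The sponsor gives up a significance claim for duration after a failed primary, which the protocol already rules out.
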